## 10.9. Appendix 9: Japanese Dermatological Association Severity Index

A. Evaluation of skin symptoms:	Erythema, pustule, edema (0-9)		
B. Evaluation of systemic symptoms/laboratory findings:	Fever, WBC count, serum CRP, serum albumin (0-8)		
○ Severity classification: (total score)	Mild (0-6)	Moderate (7-10)	Severe (11-17)

### A. Evaluation of skin symptoms (0-9)

	Severe	Moderate	Mild	None
Area of erythema (whole)*	3	2	1	0
Area of erythema with pustules**	3	2	1	0
Area of edema**	3	2	1	0

\* % relative to the body surface area (severe,  $\geq 75\%$ ; moderate,  $<75\%, \geq 25\%$ ; mild,  $<25\%$ )

\*\* % relative to the body surface area (severe,  $\geq 50\%$ ; moderate,  $<50\%, \geq 10\%$ ; mild,  $<10\%$ )

### B. Evaluation of systemic symptoms/laboratory findings (0-8)

Score	2	1	0
Fever ( $^{\circ}\text{C}$ )	$\geq 38.5$	$<38.5, \geq 37$	$<37$
WBC count ( $/\mu\text{L}$ )	$\geq 15,000$	$<15,000, \geq 10,000$	$<10,000$
CRP (mg/dL)	$\geq 7.0$	$<7.0, \geq 0.3$	$<0.3$
Serum albumin (g/dL)	$<3.0$	$\geq 3.0, <3.8$	$\geq 3.8$

## **10.10. Appendix 10: Protocol Amendment History**

This is an original protocol.

2	4 April 2025	4.3.4.6. DLQI: Removed the analysis of the number and proportion of participants with an improvement of 5 or more points from baseline in DLQI score with baseline score ≥ 5 4.5.1. Extent of Exposure: Removed the analysis of cumulative dose and newly added the summary of average of daily dose	Removed to be consistent with the analysis of other 77242113PsO study. Updated to more reasonable parameter for interpreting of extent exposure
		4.5.3.5. PHQ-9: Added the detailed definition of severity for PHQ-9 score. The description of shift table from baseline to post-baseline was updated.	Added more detailed score definition and updated the description of shift table to be consistent with other 77242113PsO study.
		6.5. Appendix 5 Prior/Concomitant/Follow-up Medications (including dictionary): Removed the analysis of concomitant treatment of moisturizer for psoriasis.	Removed since the analysis of concomitant treatment of moisturizer is not needed. Concomitant moisturizers can be found in the listing of concomitant medication.
		6.6. Appendix 6 Intervention Compliance: Changed the compliance categories to “> 120%, >100 to \leq 120%, 80 to \leq 100%, and < 80%”	Updated to more reasonable compliance categories including of the threshold of 100%.
		6.2. Appendix 2 Baseline Characteristics and Demographics Age categories of <65 and \geq 65 were added as demographic baseline variables.	Added an age category to better understand the demographics
		4.5.2. Adverse Event, clarified the description of treatment emergent adverse event as “In general, any AE occurring at or after the initial administration of study intervention up to 4 weeks after the last dose or treatment discontinuation is considered to be treatment emergent.”	Further clarifications.
		4.2.2.2. supplemental estimand, ICE #2 description is updated for further clarification, and appendix 8 is added related to this update.	Further clarification of supplemental estimand.
		4.1.2 Baseline description is updated for further clarifications	Further clarifications.

SAP Version	Approval Date	Change	Rationale
		4.1, “The specific analysis for adolescent participants (ex. CDLQI) will be performed only when at least one adolescent participant appears in the analysis set” is added.	Further clarifications for the case no adolescent participants are enrolled.

LIST OF ABBREVIATIONS

ADA	antidrug antibody
AE	adverse event
ATC	anatomic and therapeutic class
BMI	body mass index
BSA	body surface area
CI	confidence interval
CRF	case report form
CTCAE	Common Terminology Criteria for Adverse Events
CV	coefficient of variation
ECG	electrocardiogram
EP	erythrodermic psoriasis
FAS	full analysis set
GPP	generalized pustular psoriasis
ICE	Intercurrent Event
IQ	interquartile
JDA	Japanese Dermatological Association
LLOQ	lower limit of quantification
MedDRA	Medical Dictionary for Regulatory Activities
NAb	neutralizing antibodies
PD	pharmacodynamic(s)
PK	pharmacokinetic(s)
SAE	serious adverse event
SAP	statistical analysis plan
SAS	Safety analysis set
SD	standard deviation
US NCI	United States National Cancer Institute
WHO-DD	World Health Organization Drug Dictionary

1. INTRODUCTION

This Statistical Analysis Plan (SAP) contains definitions of analysis sets, derived variables and statistical methods for analyses of efficacy, safety, pharmacokinetic (PK) and pharmacodynamics (PD) data of study JNJ-77242113PSO3005.

1.1. Objectives, Endpoints and Estimands

Objectives and Endpoints

Objectives	Endpoints
Primary	

 To evaluate the efficacy of JNJ-77242113 in participants with generalized pustular psoriasis (GPP) or erythrodermic psoriasis (EP) 	
 Proportion of participants with GPP who experience treatment success (based on Clinical Global Impression [CGI] according to Japanese Dermatological Association [JDA] total score) at Week 16. Proportion of participants with EP who experience treatment success (based on CGI) at Week 16.
Secondary	

 To further evaluate the efficacy of JNJ-77242113 in participants with GPP or EP 	
 Proportion of participants with GPP or EP who experience treatment success (for GPP: based on CGI scale according to JDA total score and for EP: based on CGI scale) over time. Change from baseline in the total score of the JDA severity index for GPP over time. Change from baseline in severity classification (mild, moderate, severe) of the JDA severity index for GPP over time. Change from baseline in body surface area (BSA) of involvement of lesion for EP over time. Proportion of participants who achieve an Investigator's Global Assessment (IGA) score of cleared (0) or minimal (1) over time. Proportion of participants who achieve an IGA score of cleared (0) over time. Percent improvement from baseline in Psoriasis Area and Severity Index (PASI) over time.

 To evaluate the effect of JNJ-77242113 treatment on health-related quality of life (HRQoL) in participants with GPP or EP 	
 Change from baseline in Dermatology Life Quality Index (DLQI) score over time. Proportion of participants who achieve a DLQI score of 0 or 1 over time. Change from baseline in EQ-5D-5L (domain scores and visual analog scale [VAS]) over time.

 To assess the safety and tolerability of JNJ-77242113 in participants with GPP or EP 	
 Frequency and type of AEs and SAEs.

Objectives	Endpoints
Exploratory	
• To further explore the efficacy of JNJ-77242113 in participants with GPP	• Change from baseline in components (skin symptoms, systemic symptoms/laboratory findings) of the JDA severity index for GPP over time.
• To further evaluate the effect of JNJ-77242113 on HRQoL in adolescent participants with GPP or EP	• Change from baseline in Children's DLQI (CDLQI) over time. • Change from baseline in Children's DLQI (CDLQI) score of 0 or 1 and over time.
• To evaluate the PK and immunogenicity of JNJ-77242113	• JNJ-77242113 PK parameters. • Incidence of antidrug antibodies to JNJ-77242113.
• To explore biomarkers in participants with GPP or EP	• Change from baseline in levels of blood biomarkers.

1.2. Study Design

This is a Phase 3, open-label, multicenter study to evaluate the efficacy and safety of JNJ-77242113 for the treatment of participants with generalized pustular psoriasis (GPP) or erythrodermic psoriasis (EP).

A target of 16 (GPP, n=8; EP, n=8) participants will be enrolled in this study. All participants will take JNJ-77242113 from Week 0.

The total duration of this study for each participant is approximately 165 weeks, which includes: a ~5-week screening period, a 52-week treatment period, a 104-week long term extension treatment period (LTE), and a 4-week safety follow-up period.

All the participants will receive JNJ-77242113 200 mg once daily for 52 weeks. Participants completing Week 52 visit may be eligible to enroll in the LTE. The LTE will begin at the end of Week 52 and will continue until Week 156. All the participants will have a 4-week safety follow up period at the end of the treatment period or after the last dose of study intervention.

Efficacy, safety, PK, immunogenicity, and biomarkers will be assessed according to the Schedule of Activities in protocol Section 1.3. In addition, there will be 2 optional substudies for participants who provide consent. Sample collections for these substudies include a pharmacogenomic blood sample and photograph collection.

The first database lock (DBL) will occur when all participants complete Week 24 of the study. Additional DBLs may occur after Week 24 to support regulatory submissions and scientific disclosures.

2. STATISTICAL HYPOTHESIS

The primary hypothesis of this study is that JNJ-77242113 is efficacious in treating GPP or EP as assessed by proportion of participants with GPP and EP who experience treatment success defined

as at least "Minimally Improved" rating in CGI scale for GPP (according to Japanese Dermatological Association (JDA) total score) and EP, respectively at Week 16. No formal statistical hypothesis testing is planned in this study.

2.1. Multiplicity Adjustment

No formal hypothesis testing in this study.

3. ANALYSIS SETS

Analysis Sets	Description
Enrolled	All participants who sign the ICF
Full Analysis Set (FAS)	All enrolled participants who received at least 1 dose of JNJ-77242113.
Safety Analysis Set (SAS)	All enrolled participants who received at least 1 dose of JNJ-77242113.
PK Analysis Set	All enrolled participants who received at least 1 dose of JNJ-77242113 and had at least 1 valid blood sample drawn for PK analysis after their first dose of JNJ-77242113.
Immunogenicity Analysis Set	All enrolled participants who received at least 1 dose of JNJ-77242113 and who had at least 1 sample obtained after the first dose of JNJ-77242113 for the detection of antibodies to JNJ-77242113.

4. STATISTICAL ANALYSES

4.1. General Considerations

Data primarily will be summarized using descriptive statistics. Continuous variables will be summarized using the number of observations, mean, SD, median, interquartile range, minimum and maximum, as appropriate. Categorical values will be summarized using the number of observations and percentages as appropriate. The specific analysis for adolescent participants (ex. CDLQI) will be performed only when at least one adolescent participant appears in the analysis set.

4.1.1. Analysis Visit Windows

The schedules for visits of the study will follow per protocol 'Schedule of Activities' table. Unless otherwise specified, Nominal visits will be used for all by-visit analyses in the study.

4.1.2. Baseline

The baseline measurement for efficacy endpoints is defined as the closest measurement taken prior to or on the first study agent administration date. The baseline measurement for other endpoints including safety, PK and immunogenicity is defined as the closest measurement taken prior to the time of the first study agent administration.

4.1.3. Study Day and Relative Day

Week 0 refers to the start of the first study drug administration.

Study day or relative day for a visit is defined as:

- Visit date - (Date of Week 0) +1, if visit date is \geq date of Week 0
- Visit date - Date of Week 0, if visit date $<$ date of Week 0

4.2. Primary Endpoint Analysis

Data will be summarized based on FAS and those will be presented by diagnosed disease (GPP or EP) unless specified.

4.2.1. Definition of Endpoint

Clinical Global Impression (CGI) Score

The CGI scale is a brief clinician-rated instrument. The CGI scale has proved to be a robust measure of efficacy in many clinical drug trials, and is easy and quick to administer, provided that the clinician knows the patient well. The CGI has 5 categories (Very much improved [1], Much improved [2], Minimally improved [3], No change [4], Worsened [5]) in this study. For GPP, the rating of the CGI scale is based on JDA severity index and for EP, the rating will be as provided in the study manual.

There are 2 primary endpoints for GPP and EP respectively as given below.

For GPP:

- Proportion of participants with GPP who experience GPP treatment success at Week 16. GPP treatment success is defined as at least "Minimally Improved" rating in CGI scale according to JDA total score for GPP at Week 16.

For EP:

- Proportion of participants with EP who experience EP treatment success at Week 16. EP treatment success is defined as at least "Minimally Improved" rating in CGI scale for EP at Week 16.

4.2.2. Estimands

4.2.2.1. Primary Estimand

The primary estimand (ie, a precise definition of the primary targeted treatment effect) is defined for GPP and EP, respectively by the following 5 attributes:

Study Intervention:

- Experimental: JNJ-77242113

Population:

- Patients \geq 12 years of age with GPP
- Patients \geq 12 years of age with EP

Variable:

Binary response variables for the primary endpoints:

- Treatment success for GPP: a responder (participant with treatment success defined as at least "Minimally Improved" rating in CGI scale for GPP according to the JDA total score) at Week 16.
- Treatment success for EP: a responder (participant with treatment success defined as at least "Minimally Improved" rating in CGI scale for EP) at Week 16.

Intercurrent Events (ICE) and Their Corresponding Strategies:

Intercurrent Event	Strategy	Description
Discontinuation of study intervention for any reason on or prior to Week 16.	Treatment-policy	Observed data will be used regardless of whether or not this ICE had occurred.

Summary Measure (Population-level Summary):

- Proportion of participants with GPP who experience treatment success at Week 16.
- Proportion of participants with EP who experience treatment success at Week 16.

4.2.2.2. Supplementary Estimand

The supplemental estimand has the same attributes as in primary estimand, except for the Intercurrent events and their corresponding strategies:

Intercurrent Event	Strategy	Description
1. Discontinuation of study intervention for any reason on or prior to Week 16.	Composite	Participants with these intercurrent event are considered as nonresponders. The occurrence of these intercurrent events is captured in the variable definition.
2. Initiation of other medication or therapy that could improve GPP/EP on or prior to Week 16 excluding medication or therapy that allowed in the protocol.		
3. Discontinuation of study intervention for reasons other than ICE 1	Treatment Policy	Observed data will be used regardless of whether or not this intercurrent event had occurred.

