### **7. DISCONTINUATION OF STUDY INTERVENTION AND PARTICIPANT DISCONTINUATION/WITHDRAWAL**

#### **7.1. Discontinuation of Study Intervention**

If a participant discontinues study intervention for any reason before the end of the study, then the ET Visit assessments must be obtained (Section 1.3) as soon as possible. Study intervention assigned to the participant who discontinued study intervention may not be assigned to another participant (Section 6.2). Additional participants will not be entered in this study. Participants who discontinue study intervention but do not terminate study participation will continue to return for protocol specified procedures and evaluations. Discontinuation from study intervention does not mean that the participant is required to withdraw informed consent and leave the study.

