### 7.1.2. Temporary Interruption (Withholding) of Study Intervention

Some possible reasons for temporarily withholding study intervention include, but are not limited to, the following:

- The participant develops a serious infection.
- The participant is suspected of having tuberculosis infection (Section [8.3.7](#)).
- The participant has a hepatic event or liver test abnormality per [Appendix 5: Liver Safety: Suggested Actions and Follow-up Assessments](#).
- The participant has a PHQ-9 score of  $\geq 20$  (Section [8.3.5](#)).

Cases that may merit temporary withholding of the study intervention should be discussed with the medical monitor. The medical monitor, in consultation with the investigator, will determine when it is appropriate to recommence study intervention.

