### **8.3.5. Depression Screening and Symptoms Monitoring**

The PHQ-9 is a self-administered, 9-item questionnaire measuring symptoms and severity of depression. The recall period for all items is the past 2 weeks. The items include diminished interest or pleasure, depressed mood, insomnia/hypersomnia, fatigue or loss of energy, weight loss or weight gain/appetite loss or appetite gain, feelings of worthlessness, diminished concentration/indecisiveness, psychomotor agitation/retardation, and thoughts of death/suicide. Each item is rated on a 4-point Likert scale ranging from 0 “not at all” to 3 “nearly every day.” The PHQ-9 can generally be completed in 2 to 3 minutes ([Kroenke 2001](#)).

The PHQ-9 scores for depression range from 0 to 27 with higher scores indicating worse state (more severe depressive symptoms). A score of 5 to 9 is considered to be minimal symptoms of depression. A score of 10 to 14 is considered minor depression, dysthymia, or mild major depression. A score of 15 to 19 is considered to indicate moderately severe major depression, and a score  $\geq 20$  is considered to be severe major depression.

The PHQ-9 will be completed per the Section 1.3. The PHQ-9 result should be reviewed by the site staff prior to the participant leaving the visit to assess the level of depression.

A participant who scores  $\geq 15$  on the PHQ-9 during the study suggestive of moderately severe major depression should immediately be referred to a mental health professional for further evaluation. The investigator should contact the medical monitor for discussion.

In addition, a participant who scores  $\geq 20$  on the PHQ-9 should be temporarily discontinued from study intervention (refer to Section 7.1.2.).

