### 10.5.2. Liver Chemistry Stopping Criteria and Follow-up Assessments

Study intervention will be temporarily interrupted (withheld) for a participant if liver chemistry stopping criteria are met. Determination of temporary interruption (withheld) versus permanently discontinuation of study intervention is described below and should be discussed with the medical monitor.

Liver Chemistry Criteria with Stopping of Study Intervention Criteria and Follow-up Assessments		
Liver Chemistry Criteria	Actions Required	Suggested Follow-up Assessments

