
 
ALT or AST <math>\geq 8 \times</math>ULN.
 
ALT or AST <math>\geq 5 \times</math>ULN but <math>< 8 \times</math>ULN that persists for <math>\geq 2</math> weeks, or that cannot be monitored for <math>\geq 2</math> weeks.
 
ALT or AST <math>\geq 3 \times</math>ULN but <math>< 5 \times</math>ULN that persists for <math>\geq 4</math> weeks, or that cannot be monitored for <math>\geq 4</math> weeks.
 
ALT or AST <math>\geq 3 \times</math>ULN associated with symptomsa (new or worsening) believed to be related to liver injury or hypersensitivity.
 
	
 
Immediately discontinue study intervention.
 
Report the event to the sponsor within 24 hours.
 
Complete an SAE data collection tool if the event also met the criteria for an SAEb.
 
Repeat liver chemistry tests within 24 to 72 hours: 
 
ALT
 
AST
 
Total bilirubin
 
Alkaline phosphatase
 
INRb (if INR measured)
 
 
 
Monitor participants weekly until liver chemistry abnormalities resolve, stabilize, or return to baseline.
 
Restart study intervention if liver event causality is determined to be “not related”, restart may be permitted upon written approval of the sponsor.
 
	
 
Viral hepatitis serologyc.
 
Obtain a serum CPK and LDH.
 
Fractionated bilirubin.
 
Obtain complete blood count with differential to assess eosinophilia.
 
Obtain blood sample for PK analysis within 3 days after the most recent dosed.
 
Record the appearance or worsening of clinical symptoms of liver injury, or hypersensitivity CRF per CRF completion guidelines.
 
Record use of concomitant medications (including acetaminophen, herbal remedies, recreational drugs and other over-the-counter medications).
 
Record alcohol use.
 

Liver Chemistry Criteria with Stopping of Study Intervention Criteria and Follow-up Assessments		
Possible Hy's Law		
Liver Chemistry Criteria	Actions Required	Suggested Follow-up Assessments

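### Does the supplementary estimand leave open how to score a participant who stops study drug temporarily and restarts before Week 16?

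*SAP*

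**What the plan says.** SAP Section 4.2.2.2 lists three intercurrent events for the supplementary estimand:

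- ICE 1, composite (nonresponder): "Discontinuation of study intervention for any reason on or prior to Week 16".
- ICE 2, composite (nonresponder): starting another treatment that could improve GPP or EP, other than those the protocol allows.
- ICE 3, treatment policy (observed data kept): "Discontinuation of study intervention for reasons other than ICE 1".

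The primary estimand (SAP 4.2.2.1) has one event, discontinuation for any reason up to Week 16, handled by treatment policy. The supplementary estimand is analysed in the same way as the primary one: count, proportion and 95% Clopper-Pearson interval by disease (SAP 4.2.3.1 and 4.2.3.2). SAP Section 2 plans no formal test.

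The protocol provides for both kinds of stop. Section 7.1 begins "If a participant discontinues study intervention for any reason before the end of the study" and then requires the Early Termination visit. Below it are Section 7.1.2, "Temporary Interruption (Withholding) of Study Intervention", and Section 7.1.3 on permanent discontinuation. Section 8.3.5 says that a participant with a PHQ-9 score of 20 or more "should be temporarily discontinued from study intervention". In Appendix 5, Section 10.5.2 opens with "Study intervention will be temporarily interrupted (withheld) for a participant if liver chemistry stopping criteria are met", its action column tells the site to discontinue at once, and the same column adds that "restart may be permitted upon written approval of the sponsor".

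**The concern.** Two things look wrong. First, ICE 3 is defined as what ICE 1 leaves over, and ICE 1 leaves nothing over. The row implies that some discontinuations keep their observed data, but the table never says which.

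Second, the obvious candidates are temporary stops. ICE 1 is not limited to permanent discontinuation, Section 7.1 of the protocol puts temporary and permanent stops under one heading, and the depression and liver sections use the verb for stops that can be reversed. A participant who was stopped, restarted and improved on drug at Week 16 could then be a nonresponder on one reading and a responder on the other.

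This is the only alternative estimand planned for the primary endpoint, the groups are very small, and the study is open label. A rule chosen during programming could be chosen with the outcomes in view.

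**Working it through.** **Step 1: can ICE 3 change a result?** Up to Week 16, ICE 1 covers every reason, so the set of other reasons is empty. If the row was meant for discontinuation after Week 16, it differs from ICE 1 in timing rather than reason, and it cannot affect a Week 16 endpoint. Either way it reclassifies no one.

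**Step 2: what does unqualified discontinuation mean elsewhere in the documents?**

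| Place | Use | Points to |
|---|---|---|
| Protocol 7.1 | Stopping for any reason triggers the Early Termination visit | End of treatment |
| Protocol 1.3.2, Early Termination footnote | That visit is for participants who end study drug early | End of treatment |
| Protocol 6.7 | Completed and discontinued are paired as final states | End of treatment |
| Protocol 7.1.2 and 7.1.3 | Temporary holds have their own section and term, apart from permanent stops | Separate concepts |
| SAP 4.5.2 | Treatment-emergent window closes 4 weeks after last dose or discontinuation | End of treatment |
| SAP 4.6.1.2 | After discontinuation, all later PK data are dropped; a skipped dose removes only that visit | End of treatment, distinct from a gap |
| SAP Appendix 1 | Discontinuation, with its reasons, is a disposition category | End of treatment |
| Protocol 8.3.5 | Temporary sense, marked by an adverb and cross-referred to 7.1.2 | Loose use, flagged |
| Protocol 10.5.2 | Withholding and discontinuing used for the same stop, restart possible | Mixed |

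ICE 1 uses the same any-reason wording as Protocol 7.1. If a temporary hold counted as discontinuation there, every hold would call for an Early Termination visit. Permanent discontinuation is the natural reading.

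**Step 3: how large would the effect be if the other reading were used?** The inputs are n = 8 per group (SAP 1.2) and the Clopper-Pearson interval (SAP 4.2.3.1). The limits are

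lower = Beta⁻¹(0.025; x, n − x + 1), upper = Beta⁻¹(0.975; x + 1, n − x).

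| Responders | Proportion | 95% CI |
|---|---|---|
| 8/8 | 100% | 63.1 to 100 |
| 7/8 | 87.5% | 47.3 to 99.7 |
| 6/8 | 75.0% | 34.9 to 96.8 |
| 5/8 | 62.5% | 24.5 to 91.5 |

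Each reclassified participant moves the estimate by 1/8 = 12.5 points. Assume 7 of 8 are improved at Week 16. If 0, 1 or 2 of those 7 had a temporary stop and counted under ICE 1, the result is 87.5%, 75.0% or 62.5%. On the permanent-only reading it is 87.5% each time.

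**Step 4: how likely is a case?** The documents give no interruption rate. Let r be an assumed rate by Week 16 and assume 75% of those interrupted are improved. The chance of at least one affected participant in a group of 8 is 1 − (1 − 0.75r)⁸:

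- r = 2%: 1 − 0.985⁸ = 11.4%
- r = 5%: 1 − 0.9625⁸ = 26.3%
- r = 10%: 1 − 0.925⁸ = 46.4%

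These figures apply r to every interruption, so they overstate the doubtful cases. Holds for serious infection or suspected tuberculosis are called withholding (Protocol 7.1.2 and 8.3.7). The loosely worded cases are PHQ-9 of 20 or more and the liver criteria, and entry already excludes PHQ-9 of 15 or more and AST or ALT above 2×ULN (Protocol 5.2). In the Phase 2b study of 255 adults (Protocol 2.2), 6 stopped for adverse events, one of them for raised transaminases: 6/255 = 2.4% and 1/255 = 0.4%, with all participants as denominator. That study was in plaque psoriasis and counts discontinuations rather than holds, so it is only indicative, but it lends no support to the 10% figure.

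**The case for a change.** The strongest case for acting is that no sentence carries the permanent-only reading into the ICE table. The PK rules show that the SAP can separate discontinuation from a missed dose when it wants to, and here it did not. Version 2 of the SAP revised this same section to clarify ICE 2 and left ICE 1 and ICE 3 as they stand. With open-label data and 8 per group, a written rule is better than an inferred one, and the edit would be short.

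Part of this stands. ICE 3 is redundant, and the word permanent is missing from ICE 1. The rest carries less weight. The reading has support in both documents, including the SAP's own PK, adverse-event and disposition rules. Participants who discontinue study drug are listed individually (SAP Appendix 1), so at this sample size the classification can be checked against a listing. Treatment success is also reported at every postbaseline visit, Week 16 included, on observed data without imputation (SAP 4.3.4 and 4.3.4.1), and that summary does not depend on ICE 1.

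Rewriting ICE 3 as temporary interruption with restart by Week 16 would also open a gap of its own. A participant still on hold at Week 16 who restarts later would fall under neither that row nor a permanent-only ICE 1.

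**Conclusion.** No change to the plan is needed. ICE 3 is a leftover row that classifies nobody, and the missing qualifier in ICE 1 is a detail an analyst would fill sensibly as permanent discontinuation. On that reading the supplementary analysis is well defined and sound.

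The most that could turn on the wording is 12.5 points per affected participant, in one descriptive supplementary proportion whose 95% interval at 7/8 already runs from 47.3% to 99.7%. If nobody has a temporary stop with restart before Week 16, the two readings give the same answer. The primary estimand keeps observed data under either reading, and no test depends on the result.

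The conclusion rests on reading ICE 1 in line with Protocol 7.1 and SAP 4.5.2, 4.6.1.2 and Appendix 1. The interruption rates, the 75% improved and the 7 of 8 responders are assumptions used only to show scale. Nothing here bears on when study drug should be stopped or restarted.
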